Study Protocol

**Association Between Body Roundness Index and
Wound Healing Post-Thoracic Surgery: A Prospective
Study**

NCT ID not yet assigned

Unique Protocol ID: TJ-JRB202503009

Data:2025.05.01

Background

The thorax is a vital region of the human body, and the issue of postoperative wound healing following thoracic surgery has long been a subject of clinical concern. Thoracic surgeries—including cardiac surgery, thoracoscopic procedures, and open thoracotomy—are commonly performed for the treatment of cardiopulmonary diseases, tumors, and trauma. Although advancements in surgical techniques and medical equipment have significantly improved surgical success rates, complications such as wound infection, dehiscence, and poor cosmetic outcomes remain relatively common due to the high tension and extensive movement associated with the thoracic region[3]. Poor wound healing in the chest can have a profound impact on patients' psychological well-being, social interactions, and overall quality of life[4]. Excessive tension in soft tissues and skin is considered a key factor contributing to delayed healing and unfavorable scarring. Studies have identified gender, age, and the use of anticoagulants as risk factors for impaired wound healing, while serum lipids may play a protective role. Lipids are critically involved in modulating inflammation, angiogenesis, cellular proliferation, and tissue regeneration, all of which are essential processes in wound healing[5][9].

Obesity has emerged as a growing concern in modern medicine and now poses a serious threat to the health of a large proportion of the population. According to the *Chinese Guidelines for the Diagnosis and Treatment of Obesity*[7], both overweight and obesity exert profound negative effects on multiple organ systems, including the cardiovascular, respiratory, and gastrointestinal systems. Numerous studies have identified excessive obesity as a major risk factor for cardiovascular and cerebrovascular diseases, type 2 diabetes, and chronic kidney disease. In clinical practice, body mass index (BMI) is commonly used to assess obesity[17-19]. However, BMI has several limitations, as it cannot

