distinguish between lean body mass and fat mass, nor can it accurately reflect fat distribution throughout the body[7][21]. Recent research by Xiaoqian Zhang and colleagues has shown that the Body Roundness Index (BRI), a novel anthropometric measure, is closely associated with all-cause mortality in the U.S. population. Similarly, the Weight-Adjusted Waist Index (WWI) has gained increasing attention as a new parameter for evaluating body composition, due to its improved accuracy in estimating fat content and its strong correlation with various metabolic risk factors[22].

Recent studies have further confirmed that the Weight-Adjusted Waist Index (WWI), as an indicator of body fat distribution, demonstrates superior predictive value for various conditions, including cardiovascular and cerebrovascular diseases, chronic kidney disease, and urgency urinary incontinence (UUI)[17][23][24]. Despite advances in medical technology and a growing understanding of wound healing among healthcare professionals, postoperative wound complications remain a persistent issue. Although numerous new techniques, materials, and management strategies have been developed to promote wound healing, the incidence of poor wound healing continues to be a significant clinical concern[1][2][9][10].

Objective

By analyzing the associations between factors such as height, smoking history, age, BMI, BRI, waist-to-hip ratio, and lipid profiles with postoperative wound healing, this study aims to elucidate how these variables influence the wound healing process. Understanding these relationships will help identify novel therapeutic targets and support the development of innovative interventions to promote more efficient and effective skin wound healing.

Study Design

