The research team conducted discussions and analyses to develop the study protocol, including inclusion and exclusion criteria and the clinical data required for statistical analysis. Clinical and follow-up data of enrolled subjects were collected through the HIS system of Tongji Medical College. Using SPSS version 26.0, subjects were grouped based on whether their wounds achieved secondary healing, and intergroup differences were analyzed to preliminarily identify potential factors associated with impaired wound healing. Subsequently, logistic regression analysis was performed to further determine risk factors influencing wound healing. Multivariate logistic regression analysis was then conducted to identify independent risk factors affecting wound healing. These findings aim to provide clinically feasible intervention strategies to promote more efficient and effective wound healing.

Participant Selection

Inclusion Criteria:

- Patients who underwent surgical treatment in the Department of Thoracic Surgery at Tongji Hospital;
- Complete clinical data and diagnostic test results available;
- Postoperative follow-up conducted regularly in accordance with medical advice, with comprehensive follow-up records;

Exclusion Criteria:

- Without surgery or transferred to other departments;

- Missing basic information;
- Failure to review on time or refusal to follow up;
- Additional surgeries within 30 days of discharge from the hospital;

Sample Size Calculation

A total of 400 patients undergoing thoracic surgery in the Department of Thoracic Surgery at Tongji Hospital, affiliated with Tongji Medical College of Huazhong University of Science and Technology, will be enrolled.

Study Procedure

The research team conducted a thorough literature review to gain a comprehensive understanding of the relevant background before initiating the study design. Inclusion and exclusion criteria, as well as the clinical data required for statistical analysis, were established accordingly. A total of 500 participants are planned for enrollment; subjects not meeting the exclusion criteria will be excluded.

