Data collection and follow-up will be conducted using the HIS system of Tongji Hospital. The variables to be collected include gender, age, height (m), weight (kg), waist circumference, abdominal circumference, hip circumference (cm), comorbidities (such as hypertension, coronary heart disease, diabetes), preoperative cholesterol, triglycerides, low-density lipoprotein (g/L), and type of surgery.

Data analysis will be performed using SPSS version 26.0. Initially, independent t-tests will be applied to compare groups based on wound healing status (healed vs. secondary healing) at 30 days postoperatively to identify potential factors associated with impaired wound healing. Variables identified as significant in univariate logistic regression analysis will be entered into a multivariate

logistic regression model. Statistical significance is set at $p < 0.05$. This analysis aims to determine independent risk factors for poor chest wound healing and to propose preventive measures accordingly, culminating in the completion of the study report.

Potential Risks and Mitigation Strategies

This study is observational in nature, with data collected exclusively by inpatient physicians at our hospital. Patient privacy will be strictly protected throughout the data collection process. If any issues related to poor wound healing arise during follow-up, the follow-up personnel will inform patients of appropriate subsequent treatment options. Patients lost to follow-up will be excluded from the study.

Data Collection and Statistical Analysis

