Upon admission, patient data including gender, age, height (m), weight (kg), waist circumference, abdominal circumference, hip circumference (cm), comorbidities (such as hypertension, coronary heart disease, diabetes), and preoperative laboratory values including cholesterol, triglycerides, and low-density lipoprotein (g/L) will be collected. Postoperatively, data on the surgical procedure and routine pathological findings will be recorded. Wound healing status will be assessed during a follow-up visit 30 days after surgery. Group comparisons based on wound healing status (healed versus secondary healing) at 30 days will be performed using independent t-tests. Potential factors influencing wound healing will be evaluated using logistic regression analysis. Variables demonstrating statistical significance in univariate analysis will be included in a multivariate logistic regression model. A p -value < 0.05 will be considered statistically significant. This analysis aims to identify independent

risk factors associated with poor chest wound healing and to propose feasible preventive measures accordingly.

References

- [5] Schlager JG, Hartmann D, Wallmichrath J, Ruiz San Jose V, Patzer K, French LE, Kendziora B.

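### The univariate entry rule can put total cholesterol and its own LDL component in one model, so a real lipid association can be labelled not independent

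*Protocol*

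**What the plan says.** The Objective names lipids among the factors to be studied: "By analyzing the associations between factors such as height, smoking history, age, BMI, BRI, waist-to-hip ratio, and lipid profiles with postoperative wound healing". The Background gives an expected direction: "while serum lipids may play a protective role".

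The lipid candidates appear under Study Procedure and again under Data Collection and Statistical Analysis, where "preoperative laboratory values including cholesterol, triglycerides, and low-density lipoprotein (g/L) will be collected".

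The route into the final model is also stated twice. Study Procedure has "Variables identified as significant in univariate logistic regression analysis will be entered into a multivariate" logistic model. Data Collection and Statistical Analysis has "Variables demonstrating statistical significance in univariate analysis will be included in a multivariate logistic regression model". The threshold is "A p -value < 0.05 will be considered statistically significant". Study Design gives the purpose of the last step: "Multivariate logistic regression analysis was then conducted to identify independent risk factors affecting wound healing".

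Neither statement of the rule makes an exception for measures that overlap. The protocol does not choose one lipid measure or provide for a joint test of the lipids.

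**The concern.** Cholesterol listed beside triglycerides and LDL is naturally total cholesterol, although the protocol does not use that term. LDL cholesterol is a component of it, so the overlap is built into the definitions and is not an accident of one sample.

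If LDL is related to healing, TC tends to show the association too. When both reach the threshold, the rule places both in one model and reads each Wald p-value as evidence for or against independence. With TC held fixed, raising LDL means lowering the rest of cholesterol by the same amount. The LDL test then answers a substitution question, which is not the association that the Objective asks about, and it answers with a much larger standard error. What is at stake is a report that lipids are not an independent factor when one of them is.

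**Working it through.** **The plan's own figure.** The protocol gives 400 patients under Sample Size Calculation and 500 under Study Procedure, with no event rate, effect size or power. No power figure can be reproduced, and every rate below rests on assumptions. The 400/500 difference is a separate matter; n = 400 is used unless stated.

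**What the coefficients mean.** For any two coefficients a and b,

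a·LDL + b·TC = (a + b)·LDL + b·(TC − LDL).

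The two forms fit identically. In the TC + LDL model, a is the LDL effect minus the non-LDL effect, and b is the non-LDL effect at fixed LDL. In the form with LDL and TC − LDL, the LDL term is the LDL effect itself at fixed non-LDL cholesterol.

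**Correlation and variance inflation.** Assumed SDs in mmol/L: LDL 0.8, HDL 0.3, triglycerides (TG) 0.9, with TC = LDL + HDL + TG/2.2. The SD of TG/2.2 is 0.9/2.2 = 0.409.

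- Independent fractions: Var(TC) = 0.640 + 0.090 + 0.167 = 0.897, SD 0.947. So r(TC, LDL) = 0.8/0.947 = 0.84. VIF = 1/(1 − r²) = 3.5, and the standard error is multiplied by √3.5 = 1.87.
- Correlated fractions (LDL-TG 0.2, HDL-TG −0.4): Cov(LDL, TC) = 0.640 + 0.2 × 0.8 × 0.409 = 0.705. Var(TC) = 0.897 + 2 × 0.0655 − 2 × 0.0491 = 0.930, SD 0.964. So r = 0.705/(0.8 × 0.964) = 0.91. VIF is about 6.1, and the standard error is multiplied by √6.1 = 2.47. If triglycerides also enter, the VIFs for LDL and TC are 10-12.
- LDL with TC − LDL in the correlated case: VIF about 1.04.

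**Simulation of the written rule.** Each simulated study fits a univariate logistic model for LDL and for TC at two-sided 0.05. If both pass, both enter a joint model; if one passes, it enters alone. Inputs: n = 400, 10-20% secondary healing, true LDL odds ratio 0.55-0.65 per SD, r = 0.84-0.91.

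| Quantity | Range over scenarios |
|---|---|
| Both enter the joint model | about 56-99% |
| Neither significant, given that both enter | about 25-77% |
| At least one lipid significant at the end, all studies | about 30-75% |
| LDL significant when entered with TC − LDL, all studies | about 72-100% |

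Repeat runs move the end-points by a few points; one put the weakest corner of the last row (10% events, odds ratio 0.65) at 66-71%.

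**Sensitivity to the correlation.** With n = 400 or 500 and the same odds ratios, neither term is significant, given that both enter, in 17-70% at r = 0.84 and 42-79% at r = 0.91. A wider grid used n = 400, 5-20% events, and an effect carried by LDL or shared with TC:

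| r | OR 1.5 per SD | OR 2.0 per SD |
|---|---|---|
| 0.80 | 47-79% | 9-66% |
| 0.90 | 69-89% | 34-79% |
| 0.95 | 81-90% | 59-85% |

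With n = 500, 10% events and odds ratio 1.5, the figure is 60-85%.

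**Other remedies.** At n = 400, 10% events and odds ratio 1.5, the written rule leaves a significant lipid in 0.33-0.42 of studies at r = 0.80, 0.23-0.28 at 0.90 and 0.18-0.19 at 0.95. LDL as the single lipid term gives 0.64-0.68. A two-degree-of-freedom likelihood-ratio test of both lipids gives 0.56-0.60.

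The simulations contain no other covariates, and triglycerides do not compete for entry.

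**The case against.** The strongest reply has four parts.

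*Joint entry is conditional, and the damage depends on unknowns.* This stands. A reader might infer that a real lipid effect will as a rule be erased. The documents do not support that, because they give no event rate, effect size or correlation. At r = 0.80 with an odds ratio of 2.0 and 20% events, neither term is significant in as few as 9% of the studies where both enter.

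*The lipid objective survives.* This also stands. The Objective speaks of associations, and the group comparisons and univariate logistic results for each lipid are still produced. What suffers is the claim about independence. Lipids are also one factor among several; the exposure in the title is the Body Roundness Index.

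*The TC coefficient is meaningful.* Correct. A reader might infer that neither coefficient measures anything, or that an unstable sign on TC is itself a harm. The identity in the working shows otherwise. The TC coefficient is the non-LDL effect at fixed LDL, and the same coefficient, with the same sign, appears under the remedy. Only the LDL term changes its question and its precision.

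*Collinearity handling belongs in a statistical analysis plan.* In general it may, and that plan is not shown here. But the entry rule is written into the protocol twice without exception, so a plan that kept TC and LDL apart would contradict it. This part does not dispose of the point.

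**Conclusion.** The concern holds in a limited form. The stated rule places total cholesterol and LDL together whenever both are univariately significant, and the separate Wald tests can then hide a real lipid association. Under the assumed n = 400, 10-20% secondary healing, LDL odds ratio 0.55-0.65 per SD and correlation 0.84-0.91, the chance that any lipid remains significant is about 30-75%, against about 72-100% for LDL in the alternative form. The loss grows with the TC-LDL correlation and shrinks with a larger effect or more events. It rests on reading cholesterol as total cholesterol and on inputs that the protocol does not supply. It weakens the lipid conclusions at the multivariable step only, and says nothing about the body-size indices.

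**What to change.** Under both Study Procedure and Data Collection and Statistical Analysis, state that total cholesterol and LDL will not be entered in the same multivariable model. Then fix one of three options before outcomes are analysed:

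- LDL and non-LDL cholesterol (total cholesterol minus LDL) as prespecified lipid terms;
- one prespecified lipid measure;
- a joint test of the lipid terms in place of separate p-values.

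The sentence should also say whether the prespecified terms enter regardless of the univariate screen. The 72-100% figure assumes that they do.

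The cost is one sentence in each place and, for the first option, one derived variable. No new data are needed. The small downside of keeping the two apart is that total cholesterol is reported in its own model, not adjusted for LDL.

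### The t-test is the only comparison named for healed against secondary-healing patients and is not limited to continuous variables; for a nominal variable with three or more levels its p-value would depend on arbitrary codes

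*Protocol*

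**What the plan says.** The Study Procedure section of the protocol sets the first analysis step: "Initially, independent t-tests will be applied to compare groups based on wound healing status (healed vs. secondary healing) at 30 days postoperatively". The Data Collection and Statistical Analysis section repeats it: "Group comparisons based on wound healing status (healed versus secondary healing) at 30 days will be performed using independent t-tests". Neither sentence restricts the test by type of variable, and no chi-square, Fisher or rank test is named anywhere in the protocol.

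The list of variables to be collected contains continuous measures, but also gender, several comorbidities and, at its end, "preoperative cholesterol, triglycerides, low-density lipoprotein (g/L), and type of surgery". The later section adds that after the operation "data on the surgical procedure and routine pathological findings will be recorded".

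The Study Design section describes the purpose of this step: "intergroup differences were analyzed to preliminarily identify potential factors associated with impaired wound healing". Selection for the multivariable model is a separate step. Study Procedure ties it to logistic regression: "Variables identified as significant in univariate logistic regression analysis will be entered into a multivariate" model. Data Collection and Statistical Analysis first says "Potential factors influencing wound healing will be evaluated using logistic regression analysis" and then "Variables demonstrating statistical significance in univariate analysis will be included in a multivariate logistic regression model".

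**The concern.** A t-test compares means. For waist circumference or a lipid value the mean has a meaning. For a nominal variable stored as 1, 2, 3 it does not: the mean is a property of the numbering, and renumbering the same patients changes both the difference and its p-value.

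Type of surgery is the clearest candidate, and routine pathological findings may be another. An analyst who follows the text literally could list type of surgery as a potential factor or leave it off because of the order in which the categories were typed in. What is at stake is a missed factor on the preliminary list. The t-test is a method that the protocol names twice without restriction, so this is more than a detail left open for a later analysis plan.

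**Working it through.** **Inputs.** The protocol gives no figure to reproduce here: no event rate, no number of surgery levels and no frequencies. From the protocol come N = 400 (Sample Size Calculation; Study Procedure gives 500) and the 0.05 level, taken as two-sided. Assumed for illustration: three levels A, B, C with 200, 120 and 80 patients, and secondary healing in 10, 18 and 4 of them (5%, 15%, 5%). That makes 32 cases and 368 healed patients (190, 102, 76).

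**Pooled t-test.** t = (mean code in cases − mean code in healed) / [s × √(1/32 + 1/368)], with 398 degrees of freedom and √(1/32 + 1/368) = 0.1843.

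| Codes A, B, C | Mean, cases | Mean, healed | Pooled s | t | p |
|---|---|---|---|---|---|
| 1, 2, 3 | 58/32 = 1.813 | 622/368 = 1.690 | 0.782 | 0.85 | 0.397 |
| 2, 1, 3 | 50/32 = 1.563 | 710/368 = 1.929 | 0.695 | −2.87 | 0.0044 |
| 1, 3, 2 | 72/32 = 2.250 | 648/368 = 1.761 | 0.864 | 3.07 | 0.0023 |

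The patients are the same in all three rows; only the labels differ. The unequal-variance version does not help (p = 0.319, 0.0084, 0.0061).

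**Chi-square on the same table.** Expected cases are 32 × 200/400 = 16, 9.6 and 6.4; expected healed are 184, 110.4 and 73.6. The sum of (observed − expected)²/expected is 2.25 + 7.35 + 0.90 + 0.196 + 0.639 + 0.078 = 11.41 on 2 degrees of freedom, p = 0.0033 under any coding.

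**Two levels.** Merging A and C gives 14 cases in 280 against 18 in 120. Pooled t gives p = 0.0007 and chi-square 0.0007. For a binary variable, recoding changes nothing and the two tests nearly coincide, so gender and yes/no comorbidities are practically unaffected.

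**Rejection rates.** Simulated with 200/120/80 patients, 20,000 runs, two-sided 0.05:

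| True rates A/B/C | t, codes 1,2,3 | t, codes 2,1,3 | t, codes 1,3,2 | Chi-square |
|---|---|---|---|---|
| 5/15/5% | 9.0% | 80.2% | 84.2% | 83.4% |
| 5/10/15% | 78.8% | 17.1% | 43.0% | 70.8% |
| 8/8/8% | 5.1% | 4.4% | 5.0% | 4.8% |

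With no association every coding stays near 5%. With an association, power depends heavily on the labels. At N = 500, with 5, 45 and 5 cases in 100, 300 and 100 patients, codes 1, 2, 3 give p = 1.000 and codes 1, 3, 2 give 0.0013, against chi-square 0.0022.

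**The case against.** The strongest reply is that several conditions must hold together, and the protocol states none of them: that type of surgery is screened at all, that it has three or more levels, that its integer codes are put through a t-test, and that the chosen codes hide a true association. The variable appears on a collection list. The Objective section names height, smoking, age, adiposity indices and lipids as factors to be analysed, and not surgery, although that list is open-ended. The three kinds of surgery in the Background are general context and not this study's coding. The title exposure, body roundness index, is continuous and suits a t-test. The illustrations are also chosen to show the effect: rates that peak in the middle level nearly cancel under codes 1, 2, 3, and some codings match or beat chi-square.

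All of that stands as a limit on size. It does not remove the point, because the text names one test without restriction for a study that collects categorical variables.

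A reader might infer more, in four ways that the document does not support:

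- That false positives are inflated. They are not; the rate stays near 5%.
- That the t-test decides entry to the multivariable model. Study Procedure names univariate logistic regression for that.
- That the two sections contradict each other on entry. The later section's univariate analysis most naturally means the logistic regression in the sentence before it.
- That the protocol is at fault for not saying how type of surgery is coded in the logistic models. A single numeric term there would be code-dependent too, but factor coding is commonly left to the statistical analysis plan, which is not shown.

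**Conclusion.** The point holds in a limited form and is minor. The protocol fixes the t-test as its only healed against secondary-healing comparison without limiting it to continuous variables. Applied to a nominal variable with three or more levels, the result depends on arbitrary codes: in the assumed table p runs from 0.0023 to 0.397, and in the simulations power runs from 9.0% to 84.2% at true rates of 5/15/5%. These figures show what can happen; they do not estimate an effect in this study, since the level sizes, event counts and rates are all assumed.

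The conclusion rests on two assumptions that the protocol does not settle: that such a variable is screened with the t-test, and that it has three or more levels. If it has two, the problem does not arise. The direct consequence is a factor missed on the preliminary list; the later univariate logistic regression remains the stated route into the model.

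**What to change.** In both Study Procedure and Data Collection and Statistical Analysis, replace the t-test sentence with:

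*Continuous variables will be compared between the healed and secondary-healing groups at 30 days with independent t-tests; categorical variables, including type of surgery, will be compared with the chi-square test, or Fisher's exact test where an expected count is below 5.*

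This needs no new data and no change to the sample size. There are two small statistical costs. Fisher's exact test is slightly conservative in sparse tables: its exact type I error is 2.4% to 4.3% for a two-level variable with 20 to 60 cases in 400 patients and a prevalence of 5% to 30%. Chi-square also gives up some power if the codes happen to follow the order of risk (70.8% against 78.8% in the 5/10/15% example).

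### The p-value rule for covariates may put obesity-related comorbidities beside BRI, so the adjusted BRI odds ratio has no meaning fixed in advance, and no confounder-adjusted BRI estimate without them is planned

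*Protocol*

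**What the plan says.** The protocol title presents BRI as the exposure: "Association Between Body Roundness Index and" wound healing. The Objective is broader. It lists BRI with height, smoking history, age, BMI, waist-to-hip ratio and lipids, and says "this study aims to elucidate how these variables influence the wound healing process".

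The Background gives this account of obesity: "Numerous studies have identified excessive obesity as a major risk factor for cardiovascular and cerebrovascular diseases, type 2 diabetes, and chronic kidney disease".

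Data Collection and Statistical Analysis lists among the data "comorbidities (such as hypertension, coronary heart disease, diabetes"), and records them at the same time as the body measurements: "Upon admission, patient data including gender, age, height (m), weight (kg), waist circumference, abdominal circumference, hip circumference (cm), comorbidities". The rule for the multivariable model is "Variables demonstrating statistical significance in univariate analysis will be included in a multivariate logistic regression model", with the threshold "A p -value < 0.05 will be considered statistically significant". Study Procedure gives the same rule and states its purpose: "This analysis aims to determine independent risk factors for poor chest wound healing and to propose preventive measures accordingly".

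No variable is forced into the multivariable model or kept out of it. Possible confounders of BRI are not distinguished from its possible consequences. The univariate step does give one BRI odds ratio without comorbidities, but it is unadjusted.

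**The concern.** If obesity contributes to diabetes, and diabetes impairs healing, part of the BRI-healing association runs through diabetes. A BRI odds ratio adjusted for diabetes leaves that part out and describes only what remains. Both quantities are legitimate, but they answer different questions, and the protocol does not say which it wants.

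The entry rule adds a second problem. A comorbidity tends to pass the screen when it predicts healing, which is also when adjusting for it changes the BRI estimate most. Whether none, one or several enter depends on the sample. Two runs of the same study could therefore report adjusted BRI odds ratios that mean different things.

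At stake is the reading of the result that the title announces. A BRI association acting through diabetes or coronary disease could be significant in the univariate step, lose significance in the multivariable model, and be reported as BRI not being an independent risk factor. A reader looking for preventive measures could take that to mean that BRI does not matter.

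**Working it through.** **What the text supports.** The Background links obesity to cardiovascular and cerebrovascular disease, type 2 diabetes and chronic kidney disease. Against the comorbidities collected:

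- Diabetes: covered (type 2).
- Coronary heart disease: covered as a cardiovascular disease.
- Hypertension: not named; covered only if cardiovascular disease is read broadly.
- Lipids: the Background does not say that obesity alters them.

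The second link, from comorbidity to impaired healing, is not asserted in the Background and has to be assumed.

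**No stated figure to reproduce.** The protocol gives no event rate, odds ratio or comorbidity prevalence. Every input below is an assumption except the 0.05 threshold (two-sided assumed) and n = 400, the figure under Sample Size Calculation (Study Procedure says 500).

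**Measure.** Loss = 1 - ln(OR adjusted) / ln(OR total). OR total is for BRI per SD with the comorbidities left out; OR adjusted has all three in. Odds ratios also shift slightly when any predictor of outcome is added, so this only approximates the share running through the comorbidities.

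**First set of inputs.** Direct BRI OR 1.3 per SD; prevalence of diabetes 15%, hypertension 35%, coronary disease 12%; BRI-to-comorbidity OR 1.3 to 2.0 per SD; comorbidity-to-healing OR 1.0 to 3.0; event rate 5 to 20%. Odds ratios come from 400,000 simulated patients, and entry frequencies from samples of 400. At a 10% event rate and BRI-to-comorbidity OR 1.6:

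| Comorbidity OR on poor healing | Total BRI OR | Adjusted BRI OR | Loss | BRI and at least one comorbidity enter |
|---|---|---|---|---|
| 1.0 | 1.292 | 1.293 | 0% | 9% |
| 1.5 | 1.428 | 1.303 | 26% | 37% |
| 2.0 | 1.520 | 1.291 | 39% | 64% |
| 3.0 | 1.662 | 1.302 | 48% | 81% |

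Third row worked: ln(1.520) = 0.419, ln(1.291) = 0.255, and 1 - 0.255/0.419 = 0.39. In that row BRI passes the screen in 67% of samples, diabetes in 56%, hypertension in 67% and coronary disease in 48%. All four enter together in 15%.

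With comorbidity ORs of 1.5 to 3, over all event rates and BRI-to-comorbidity ORs, the loss runs from about 15% (1.363 to 1.299) to 60% (1.945 to 1.301). Joint entry runs from 12% to 100% of samples.

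**Second set, with unequal links.** n = 400, 10% events; prevalence 14%, 35% and 12%; BRI to diabetes, hypertension and coronary disease OR 1.8, 1.65 and 1.35 per SD; these to poor healing OR 2-3, 1.3-1.5 and 1.5-2; direct BRI OR 1.1-1.2. The total BRI OR of 1.21-1.41 falls to 1.09-1.22 with all three in, a loss of 33-65%.

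Applying the protocol's own screen to this second set:

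- BRI fails the univariate screen in 43-79% of samples, so it passes in 21-57%.
- BRI and at least one comorbidity enter together in 16-54%.
- A significant univariate BRI result is then lost in 10-34% of all samples.
- BRI ends significant in 11-25%, against 8-18% if all three comorbidities were forced in.

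**The case against.** **Independent risk factors are the declared aim.** Study Design, Study Procedure and Data Collection and Statistical Analysis all say so, and the Objective lists BRI among several factors. For that aim, mutual adjustment is legitimate. This stands. A reader might infer that the total BRI association is the only relevant quantity; the documents do not say that. What remains is that the title singles out BRI and the plan seeks preventive measures, without saying which BRI association is meant.

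**Entry is conditional.** A reader might infer that diabetes, hypertension and coronary disease will be in the model with BRI. The protocol says only that variables significant in univariate analysis enter, and BRI itself must pass. Figures with all three forced in therefore overstate the effect on significance. Where BRI fails the screen, the cause is limited power, which is a separate matter.

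**A comorbidity-free BRI odds ratio already exists.** The univariate step supplies it. This stands, but that estimate is not adjusted for age, gender or type of surgery and serves as a screen.

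**The Background does not cover everything.** A reader might infer that, on the protocol's own account, hypertension and lipids also lie on the path. Hypertension is not named, and for lipids the Background mentions only a possible protective role in healing.

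**Timing.** BRI and comorbidities are recorded at the same admission, so their order is not established. A comorbidity may be partly a confounder, and leaving it out is not automatically unbiased. This stands, and it argues against making the comorbidity-free model the sole main result.

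**Conclusion.** The concern holds in a limited form. The protocol fixes a covariate rule based on p-values alone, and states it in two places, so this is not a detail left to a statistical analysis plan. The rule can place diabetes and coronary heart disease, and possibly hypertension, beside BRI, which leaves the meaning of the adjusted BRI odds ratio dependent on the data. No confounder-adjusted BRI estimate without these conditions is planned.

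The size of the loss cannot be computed from the documents. Under assumed inputs it is about 0% of the log odds ratio if the comorbidities do not affect healing, and roughly 15-65% if their odds ratios are about 1.3-3. It occurs only in samples where both BRI and a comorbidity pass the screen. The data to be collected are unaffected; what is at risk is a misread null for BRI.

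**What to change.** In Study Procedure and in Data Collection and Statistical Analysis:

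1. Prespecify a BRI model with age, gender and type of surgery, fitted whatever the univariate p-values are.
2. Prespecify a second model that adds the comorbidities and lipids.
3. Report both BRI odds ratios side by side and state which association each describes: the first with the pathways through comorbidities left in, the second what remains after adjusting for them.
4. State that the second model alone will not be used to conclude that BRI is unrelated to healing.

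The search for independent risk factors can stay as a separate analysis.

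The cost is a few sentences and one additional regression; the adjustment variables are already collected. The downside is that two BRI odds ratios must be explained. Because BRI and comorbidities are recorded at the same admission, the report should also say that a comorbidity may be partly a confounder and that neither model should be read alone.
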